Appendix G. Information with regards to Safety Reporting in Non-CTIMP Research

	Who	When	How	To Whom
SAE	Chief Investigator	Report to sponsor within 24 hours of learning of the event Report to the MREC within 15 days of learning of the event	SAE report form for non-CTIMPs, available from NRES website.	Sponsor and MREC
Urgent Safety Measures	Chief Investigator	Contact the sponsor and MREC immediately Within 3 days	By phone Substantial amendment form giving notice in writing setting out the reasons for the urgent safety measures and the plan for future action.	Main REC and sponsor Main REC with a copy also sent to the sponsor. The MREC will acknowledge this within 30 days of receipt.
Progress Reports	Chief Investigator	Annually (starting 12 months after the date of favourable opinion)	Annual progress report form (non-CTIMPs) available from the NRES website	Main REC
Declaration of the conclusion or early termination of the study	Chief Investigator	Within 90 days (conclusion) Within 15 days (early termination) The end of study should be defined in the protocol	End of study declaration form available from the NRES website	Main REC with a copy to be sent to the sponsor
Summary of final Report	Chief Investigator	Within one year of conclusion of the research	No standard format However, the following Information should be included: Where the study has met its objectives, the main findings and arrangements for publication or dissemination including feedback to participants	Main REC with a copy to be sent to the sponsor

Appendix H: Echocardiographic analysis:

NOTE-AF Transthoracic Echocardiography Protocol

Introduction

The proposed Transthoracic Echocardiography (TTE) protocol for the NOTE-AF study strictly adheres to the outlined minimum data set presented by the British Society of Echocardiography (BSE) [32] with the addition of a number of novel advanced TTE metrics. The BSE minimum dataset ensures that a full and comprehensive assessment of cardiac anatomy, function and haemodynamics can be assessed on each patient enrolled within the study. When pathologies are present, additional TTE analysis can be performed (e.g., significant mitral regurgitation) on a case-by-case basis.

The TTE protocol outlined below aims to include the use of novel speckle tracking strain imaging on all four cardiac chambers. Left ventricular (LV) global longitudinal strain (GLS) is now an increasingly popular technique used to assess LV systolic function and regional wall motion abnormalities (RWMA's). Both LV GLS and strain rate have been associated with detections of subclinical cardiac disease and alterations in LV systolic function before detectable changes in ejection fraction (EF) [33]. Similarly, speckle tracking strain of the right ventricle is emerging as an increasingly popular method of assessing regional RV deformation, as it has shown to be reproducible and prognostic in a variety of conditions [34]. More recently in both research and clinical settings, speckle tracking imaging has been applied to the atria in order to better understand atrial mechanics and in efforts to detect subclinical changes. Atrial strain examines the three functions of the atria (reservoir, conduit and booster/pump). In a number of pathologies, atrial strain has shown to be impaired prior to any structural changes in LA volume, which has traditionally be used as a marker of atrial impairment [35]. Interestingly, emerging evidence is highlighting associations between strain measurements and detection of atrial arrhythmias [36-39]. In addition to this, the proposed protocol outlined below aims to assess the electromechanical delay within the atria. Studies have previously identified that the time delay between the onset of the P wave on ECG, to the beginning of the A' wave of the Tissue Doppler Imaging (TDI's) has been independently associated with atrial arrhythmia occurrence in both cardiac and non-cardiac pathologies [40-42].

In summary, the proposed protocol aims to utilise all standard TTE views outlined by a full and comprehensive level 2 study (*see Table 1*) with the addition of novel and emerging analysis techniques in order to detect subclinical, yet meaningful changes. All additional analysis outside of the minimum dataset will be performed off-line.

TTE Protocol Workflow

Image Acquisition and Analysis

It is anticipated that all TTE studies will be performed by BSE accredited echocardiographers. The TTE studies will be requested, performed and reported on as part of the usual care pathway for patients. Reports will be to the standard set out by the Cardio-Respiratory Department of the Royal Liverpool Hospital, a BSE accredited department. TTE studies will be performed using a GE S70 Vivid (GE Vingmed Ultrasound) ultrasound machine, which is the standard clinical machine used for bedside full level 2 TTE studies. TTE Additional analysis, which is outside of the outlined minimum dataset will be performed off-line using EchoPac Analysis Software (GE Vingmed Ultrasound).

Data Storage

Images obtained will be stored onto IntelliSpace Cardiovascular (Phillips Medical) alongside the formal clinical report. Additional TTE parameters which are being examined (outside that of the BSE minimum dataset) will be analysed and stored on EchoPac Analysis Software (GE Vingmed Ultrasound). All images and reports are only accessible using Liverpool NHS Foundation login credentials, as well as those granted access to IntelliSpace and EchoPac (password protection). Raw data will be extracted from images and stored in a password protected Microsoft Excel spreadsheet (Microsoft Office), accessible only by my research team members.

Table 1. Summary of TTE protocol

[figure not shown]
TTE View	Measurements/assessments
PLAX zoom out	Visual assessment of plural and pericardial space
PLAX	LV dimensions (LVEDd, LVESd, IVSd and PWDd). Visual assessment of LV and RV radial function. Left atrium dimension (Anterior-Posterior on PLAX zoom in). RVOT dimension. Visual assessment of MV structure

	(focused), colour assessment of MV. Visual assessment of AV structure (focused), colour assessment of AV. LVOT dimension. Aortic root dimensions (SOV, STJ and Prox Asc Aorta)
PLAX RV Inflow	Visual assessment of RV, TV and RA. Colour flow assessment of TV. CW Doppler assessment of TR Vmax.
PLAX RV Outflow	Visual assessment of RVOT, PV , main PA and bifurcation. Colour flow assessment of PV with CW Doppler. CW Doppler to assess PV Vmax. PW Doppler assessment in RVOT for Pulmonary acceleration time.
PSAX (aortic level)	AV Morphology. AV colour assessment. Colour assessment of IAS. Visual TV assessment and colour assessment. CW Doppler of TR (if present and measurable). RVOT 1 and RVOT 2 dimensions. PV visual assessment and colour assessment. CW Doppler of PR (if present) and PV Vmax). Main PA dimension.
PSAX (MV level)	Visual assessment of MV structure. Colour flow assessment of MV for origin of MR jet (if present). Visual assessment of RWMA's. . Colour flow assessment for VSD.
PSAX (Mid level)	Visual assessment of RWMA's. Colour flow assessment for VSD. Visual assessment of RV function.
PSAX (Apical level)	Visual assessment of RWMA's. Colour flow assessment for VSD.
A4C View.	Overall visual assessment of gross cardiac anatomy – focused (zoomed in) view used for assessment.
A4C view LA focus.	LA Biplane volume assessment. LA speckle tracking strain (reservoir, conduit and pump function). Visual MV structure assessment. Colour flow of MV assessment. Full comprehensive quantifiable MR assessment (if applicable). PW Doppler of Pulmonary veins. Colour flow assessment of IAS.
A4C view LV focus	Visual assessment of LV systolic function and RWMA's. EDV, ESV and EF

	assessment by Simpson's Biplane method. Global Longitudinal LV strain assessment. TDI assessment of lateral and medial annulus. PW Doppler of LV inflow velocities (electromechanical delay). Colour flow assessment of septum.
A4C view LV/RV focus	LV/RV basal diameter ratio
A4C view RV focus	RV basal, mid and length dimension. TDI and M mode assessment of RV longitudinal function. RV fractional area change. Global Longitudinal RV strain assessment. PW Doppler of RV inflow.
A4C view RA focus	RA area. Visual assessment of TV structure. Colour flow assessment of TR with full comprehensive quantifiable TR assessment (if applicable). CW Doppler of TR Vmax (if applicable).
A5C view.	Visual assessment of AV and LVOT. Colour flow assessment of AV. CW Doppler assessment of AR (if present) and transaortic velocities. PW Doppler assessment of LVOT.
A2C view	Overall visual assessment of gross cardiac anatomy – focused (zoomed in) view used for assessment.
A2C view LA focus	Visual assessment of LA and appendage (if visible). LA volume assessment with Biplane method. LA speckle tracking strain (reservoir, conduit and pump function). Visual MV structure assessment. Colour flow of MV assessment. Full comprehensive quantifiable MR assessment (if applicable).
A2C view LV focus	Visual assessment of LV systolic function and RWMA's. EDV, ESV and EF assessment by Simpson's Biplane method. Global Longitudinal LV strain assessment.
A3C view	Overall visual assessment of gross cardiac anatomy – focused (zoomed in) view used for assessment.
A3C view LA focus	Visual assessment of LA. Visual MV structure assessment. Colour flow of MV assessment. Full comprehensive quantifiable MR assessment (if applicable).
A3C view LV focus	Visual assessment of LV systolic function

	and RWMA's. Global Longitudinal LV strain assessment. Colour flow assessment of IVS.
A3C view AV focus	Visual assessment of AV and LVOT. Colour flow assessment of AV. CW Doppler assessment of AR (if present) and transaortic velocities.
A3C View TV tilt	Further visual assessment of TV structure. Colour flow assessment of TR. CW Doppler for assessment of TR Vmax (if applicable).
Subcostal view	Visual assessment of pericardial space, RV and LV radial function, TV and MV structure. Colour flow assessment of IAS. IVC diameter and change during inspiration (M-mode or 2D). Subcostal short axis view can be used to assessment structures outlined in PSAX view if image acquisition has been suboptimal.
Suprasternal view	Visual assessment of aortic arch structure. Dimensions of arch. Colour flow assessment. CW Doppler of descending aorta. PW Doppler of arch/descending aorta if significant gradient detected.

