Patients admitted to wards where the WARD247 application is being tested, will be asked to participate. Patients will be asked to complete a questionnaire (Appendix C) to explore their experiences with a remote wireless monitoring system. Health care professionals will participate in semi-structured interviews (Appendix A) and complete the mHealth App Usability Questionnaire (MAUQ) for Standalone mHealth Apps Used by Healthcare Providers a standard questionnaire designed by the University of Pittsburgh (Appendix B). The results and data obtained in this work package will be shared with the WARD24/7 international study team as described in a separate data sharing agreement.

Outcomes for this work package include:

- Number of false alerts
- Number of correct alerts
- MAUQ score
- Semi-quantitative assessment of patient acceptability
- Semi-quantitative assessment of acceptability for nursing and healthcare staff
- Time wCVSM is attached

Study Objectives, Design and Statistics

Research questions and objectives

The **primary research objective** is:

To determine the incidence of clinical and subclinical episodes of AF in acutely unwell patients and to generate data for the development and validation of virtual twins and clinical decision support tools.

The **secondary research objective** is:

To determine patient acceptability and usability for health care professionals of a novel remote monitoring device with automated alert function.

Primary outcome:

The incidence of episodes of AF lasting >30 seconds in acutely unwell and postoperative patients recorded as part of standard clinical care through extended remote wireless patch-based monitoring with or without the use of an alert system (Application).

Secondary outcomes:

Work package 1:

- Length of stay
- Hospital readmissions within 90 days
- Hospital and 90-day Mortality
- Recurrence of AF episodes
- Time spent in AF
- Number of AF episodes
- Complications of AF, e. g. stroke, thromboembolic events
- High sensitivity Troponin concentrations in patients with AF episodes
- Echocardiographic changes in patients with AF episodes

Work package 2:

- MAUQ score
- Percentage change of troponin concentrations in patients with and without episodes of AF
- Time (in hours) wCVSM is attached
- Number of cardiovascular alerts

- Number of non-cardiovascular alerts
- Number of alerts reflecting clinical changes
- Number of alerts reflecting artefacts or non-clinical events

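### Off-line echo measures are read with no rule to keep the reader unaware of AF status, which could bias the secondary echo comparisons

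*Protocol*

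**What the plan says.** Appendix H is the study's echo measurement protocol. On top of the national minimum dataset it "aims to include the use of novel speckle tracking strain imaging on all four cardiac chambers", discusses LV strain rate, and adds a timing measure: "the proposed protocol outlined below aims to assess the electromechanical delay within the atria". The reading of these extras is separated from the scan: "All additional analysis outside of the minimum dataset will be performed off-line", using EchoPac. Under Data Storage, "Images obtained will be stored onto IntelliSpace Cardiovascular (Phillips Medical) alongside the formal clinical report". The next step is "Raw data will be extracted from images and stored in a password protected Microsoft Excel spreadsheet (Microsoft Office), accessible only by my research team members".

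The Introduction to Appendix H gives the reason for the extra measures: "emerging evidence is highlighting associations between strain measurements and detection of atrial arrhythmias". It makes a similar statement about electromechanical delay.

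The secondary outcomes for work package 1 include "Echocardiographic changes in patients with AF episodes". LV strain rate is listed by name in the synopsis endpoints and again among the secondary outcomes. The Statistics section plans univariate comparisons of outcomes, and the synopsis sets a two-sided 0.05 level. The Echocardiography section limits scans to patients with a clinical indication and gives no expected number.

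The protocol says nothing about masking the off-line reader, the order of reading, or when values become final. The study-number and anonymisation rules under Confidentiality and Case Report Form protect identity; they do not hide AF status from a reader.

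**The concern.** Strain and electromechanical delay leave room for judgement, for example in marking where the P wave and the A' wave begin. The reading is done after acquisition and its timing is left open, so for some patients it may come after AF has been documented. A reader who knows which patients had AF, and who has been told that these measures are linked to arrhythmia, may measure the two groups slightly differently without intending to.

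A small systematic shift in one group would look like an echo marker of AF. No later analysis could separate it from a true difference, because the bias would already be in the recorded values. That is why the point belongs in the measurement protocol. Appendix H already fixes the machine, software, storage and access, but not this.

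**Working it through.** **Step 1: what the text does and does not establish.**

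| Question | Protocol |
|---|---|
| When are the extra measures read? | Off-line, after the scan; no time set relative to AF ascertainment (Appendix H) |
| Who reads them? | Not named; research team members hold the extracted data (Appendix H, Data Storage) |
| What can the reader see? | Images are stored with the clinical report; no restriction on other sources |
| Is an AF link suggested? | Yes, as an association without direction (Appendix H, Introduction) |
| Is echo in AF patients an outcome? | Yes, secondary, work package 1; LV strain rate is a named endpoint |
| Is there masking, or locking before linkage? | Neither is stated |

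The opportunity for bias follows from these entries. Its occurrence and size do not.

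**Step 2: the plan's own figure.** The protocol expects at least 60 to 120 AF patients among 1200. With its 5% risk threshold, 0.05 × 1200 = 60. The upper end corresponds to 0.10 × 1200 = 120; the 10% is inferred. The number of these patients who will have an echo is not given.

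**Step 3: illustration.** Suppose there is no true difference and the reader shifts values in AF patients by b standard deviations. For a two-group normal test at two-sided 0.05:

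SE = √(1/n_AF + 1/n_nonAF)

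Rejection rate = Φ(b/SE − 1.96) + Φ(−b/SE − 1.96)

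Both b and the echo counts are assumptions.

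- 30 AF v 300 non-AF: SE = √(1/30 + 1/300) = 0.1915. For b = 0.1, b/SE = 0.522 and the rate is 8.2%. For b = 0.2, b/SE = 1.044 and the rate is 18.1%.
- 60 AF v 300 non-AF: SE = √(1/60 + 1/300) = 0.1414. For b = 0.1, b/SE = 0.707 and the rate is 10.9%. For b = 0.2, b/SE = 1.414 and the rate is 29.3%.
- With b = 0 the rate is the nominal 5%.

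**Step 4: sensitivity to the echo counts.** Here the protocol's 60 to 120 AF cases are kept and the share of all patients scanned is varied:

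| Share scanned (assumed) | AF v non-AF | b = 0.1 | b = 0.2 |
|---|---|---|---|
| 25% | 15 v 285 to 30 v 270 | 6.6–8.1% | 11.7–18.0% |
| 50% | 30 v 570 to 60 v 540 | 8.3–11.4% | 18.7–31.2% |
| 100% | 60 v 1140 to 120 v 1080 | 11.7–18.0% | 32.7–54.7% |

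The excess over 5% appears in every row, but its size depends wholly on the assumed shift and counts.

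**The case against.** The strongest reply is that this is silence, not error. Appendix H does not tell anyone to read with knowledge of AF, and masked reading could be set in a working procedure that is not shown. There is also a good argument that the clinical report often could not reveal AF. Patients enter in sinus rhythm, and Appendix E places echo at screening and on days 1 to 3, while AF documentation continues to day 90. Subclinical episodes come from patch waveforms, and neither the monitoring server nor the study database is described as linked to the echo archive.

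Much of this stands, and it rules out several stronger readings that a reader might infer:

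- *The research team makes the measurements knowing AF status.* The team's access to the extracted data is stated. The reader's identity and the time of reading are not.
- *Appendix H states the expected direction.* It states association only. Its remark about impaired atrial strain concerns a number of pathologies, not AF.
- *Atrial strain and electromechanical delay are endpoints to be tested against AF.* They are not listed; LV strain rate is. The outcome on echo changes in AF patients is general and names no non-AF comparator.
- *A biased value will enter the risk model.* The risk factors given as examples in the Statistics section include no echo measure, although the list is open-ended.
- *The error rates are estimates for this study.* They are not. The 60 v 300 case, for instance, implies 60/360 = 16.7% with AF among those scanned, above the 5% to 10% behind the protocol's own count.

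The gap itself remains. The time of off-line reading is left open, no source of AF status is closed to the reader, and nothing fixes the values before linkage. Masking is a matter of how measurements are made, so an analysis plan cannot restore it once clips have been read.

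**Conclusion.** The point holds as a modest, inexpensive improvement to secondary measurements. The protocol specifies off-line reading of measures open to judgement, gives a reason to expect a link with arrhythmia, and makes echo findings in AF patients a secondary outcome, yet has no safeguard against knowledge of AF status. That knowledge could bias the comparisons; the documents do not show that it will.

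The illustrative range of about 8% to 29% rests on an assumed shift of 0.1 to 0.2 SD and assumed counts of 30 or 60 AF against 300 non-AF echoes. It should be read as showing that a small shift would matter, and nothing more. Scans read before any AF occurs are not exposed to this bias. The primary outcome, AF incidence, and the sample size are unaffected.

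**What to change.** Add to Appendix H, under Image Acquisition and Analysis, a rule along these lines:

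- The existing off-line reader measures clips exported under a code and in random order, without the clinical report, the notes, the wireless monitoring results or AF status.
- The values are locked before they are linked to the AF data.
- Clips that show AF on the trace are flagged, and sinus-rhythm clips form the main comparison for the strain measures. Electromechanical delay already needs a P wave, so the restriction adds little there.

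The cost is the work of coding the clips and a few lines of text. No extra scan or reader is needed, and care and sample size do not change. The limitation to acknowledge is that masking is incomplete for any clip where the rhythm trace itself shows AF.
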